5.5 Specific exclusion criteria for skin biopsies

The following criteria not allowing the biopsy samples (at baseline and week 12) will be checked at screening, only for subjects who accept skin biopsies (by signing an additional consent) :

1. The subject has history of coagulation disorders
2. The subject has known sensitivity to local anesthetics.
3. The subject is using platelet aggregation inhibitors, or anticoagulants (of note, sporadic intake or continuous low-dose intake of aspirin or other NSAIDS is allowed).
4. The subject has history or physical evidence of keloids or hypertrophic scarring resulting from skin trauma. The clinical examination will include the observation of the possible scars of the subject.

5.6 Previous and concomitant therapies

5.6.1 Definition

Previous therapies are defined as therapies that have been stopped within the 3 months before the screening visit, unless relevant to the inclusion/exclusion criteria. Whenever possible, previous therapies for PN and underlying disease(s) if any, should be documented.

Concomitant therapies are defined as follows:

- any existing therapies ongoing at the time of the screening visit,
- any changes to existing therapies (such as changes in dose or formulation) during the course of the clinical trial, or
- any new therapies received by the subject since the screening visit

5.6.2 Categories

The following two categories are to be considered for previous and concomitant therapies:

- Drugs/therapies including but not limited to, prescription, over-the-counter (OTC), birth control pills/patches/hormonal devices, vitamins, moisturizers, sunscreens, herbal medicines/supplements, and homeopathic preparations.
- Medical and surgical procedures including, but not limited to, laser/radiation procedures, dermal fillers, X-rays, etc.

5.6.3 Recording

Previous and concomitant therapies are to be recorded on the Drugs/Therapies form (for drugs/therapies) or on the Medical and Surgical Procedures form (for medical/surgical procedures) in the electronic case report form (eCRF).

Concomitant therapies are to be recorded, reviewed, and updated at each visit. Any new concomitant therapy or modification of an existing therapy may be linked to an AE. A corresponding AE form should be completed to account for the change in therapy, except in some cases such as dose modification for a chronic condition (see section [7.2.4](#)), in which case the medication will be linked to an item in the medical history.

5.6.4 Authorized concomitant therapies

Unless listed under the exclusion criteria (Section [5.4](#)) or in prohibited concomitant therapies (see Section [5.6.5](#)), all therapies are authorized.

Sedatives and antidepressants as described in [Table 3](#) are allowed if they have been administrated for at least 3 months at a stable dose before screening baseline and dose changes are not planned during the study.

Starting from the screening visit, subjects will be instructed to use their daily moisturizer, if it is not containing any compound with known anti-itch effect (such as menthol, polidocanol; etc.). It is not authorized changing emollients or moisturizers or applying products for itching relief during the course of the study.

5.6.5 Prohibited concomitant therapies

The therapies listed in Section 5.4 item [13](#) are prohibited because they may interfere with the efficacy and/or safety assessment of the study drug. If prohibited therapies become a necessary treatment for the safety or best interest of the subject, GALDERMA or its designee (i.e. Contract Research Organization (CRO)) should be notified to discuss possible alternatives prior to administration of a prohibited therapy and the pertinence and the modalities for the subject to continue in the clinical trial.

5.7 **Rescue therapies**

If deemed to be medically necessary by the Investigator, rescue treatments for pruritus could be added to the study drug from Day 29. In that case, all efficacy and safety assessments should be completed before starting the rescue treatments.

Rescue therapies should prioritize the use of antihistamines, which are commonly used and are not associated with significant side effects. If the investigator considers it necessary, occasional local treatment with TCS of mid-potency might be also combined with antihistamines.

In case of the above mentioned rescue therapies, the administration of study drug can be continued.

If the subject receives another rescue treatment for PN than the ones listed above (e.g. cyclosporine, thalidomide, gabapentin, phototherapy), the study medication must be stopped.

5.8 **Procedures/Reasons for subject discontinuation from the study**

Subjects may discontinue from the study or only discontinue the study treatment (as described in Section 6.5)

The reasons and procedures for subject discontinuation from the study are described below..

Although the importance of completing the entire clinical trial will be explained to the subjects, any subject is free to discontinue his/her participation in the study at any time and for whatever reason, specified or unspecified, and without any prejudice. No constraints are to be imposed on the subject, and when appropriate, a subject may be treated with other conventional therapy when clinically indicated. Investigators or the sponsor can also withdraw subjects from the clinical trial if deemed to be necessary.

When a subject discontinues from the clinical trial, he/she will be fully assessed whenever possible. Subjects discontinued before the week 4 visit (visit for the primary endpoint) should attend an early termination visit and a final visit 10 weeks after the last study drug injection for safety follow-up. Subjects discontinued after the week 4 visit should attend a final visit 10 weeks after the last study drug injection.

Potential reasons for study discontinuation include pregnancy, consent withdrawal by the subject, lost to follow-up, lack of efficacy, AEs, protocol deviations and others. If the reason is “consent withdrawal by the subject” or “others”, the subject will be questioned to rule out the possibility of an AE. If an AE leads to study discontinuation, AE should be chosen as the reason instead of “withdrawal by the subject” or “other”. If a subject discontinues study treatment and study participation at the same time, the reasons for those two discontinuations should be the same.

A subject who has been randomized and assigned a randomization number cannot be replaced by another subject.

GALDERMA R&D
Protocol No.: RD.03.SPR.115828
FINAL version V00 dated 30 MAY 17
Page 38 of 86

All discontinuations and the reason for discontinuation are to be documented by the Investigator on the Exit Form.

For discontinuation due to an AE, the Adverse Event Form is to be completed. The Investigator should also ensure that the subject receives suitable therapy for the AE.

GALDERMA may also decide to prematurely terminate or suspend a subject's participation in the clinical trial.

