3 OVERALL CLINICAL TRIAL DESCRIPTION

3.1 Overview

This is a randomized, placebo-controlled, double-blinded, parallel group, multicenter study to evaluate the safety and efficacy of nemolizumab in patients suffering from PN.

Approximately 70 adult patients suffering from PN for at least 6 months with severe pruritus defined by the mean of the worst daily intensity of the NRS score ≥ 7 over the previous week at baseline will be randomized in the study.

Subjects meeting inclusion/exclusion criteria will be randomized in a 1:1 ratio to nemolizumab or placebo. Each subject will receive three subcutaneous injections of 0.5mg/kg of nemolizumab or matching placebo. Injections will be administered every 4 weeks (at baseline, week 4 & week 8).

Subjects' participation in the study will be up to 22 weeks, including an up to 4-week screening period, a 12-week treatment period (last study drug injection at week 8) and a 6-week follow-up

period (10 weeks after the last study drug injection corresponding to 5 half-lives of nemolizumab).

A total of 10 visits per subject is planned. Schedule of assessments is summarized in [Table 2](#). Safety and efficacy assessments will be conducted throughout the study. Pruritus severity will be self-evaluated by the subjects on a daily basis using the ePRO and following instructions provided by the Investigator. The Investigator will evaluate the evolution of prurigo lesions using appropriate scales.

PK profile of nemolizumab in PN patients will be assessed according to [Table 2](#).

PD assessments will be performed to evaluate cytokines/chemokine profiles, IL31 and IL31 RA quantification by proteomics, genomic and histology analysis using three 4-mm skin biopsies, D-squames and blood samples collected according to [Table 2](#). Skin biopsies will be optional, patients accepting this procedure will have to sign an additional consent.

Exploratory biophysical assessments will be performed by measuring scratching events during the night and sleep duration using actigraphy. The subject will have to wear two watches from Day -7 to baseline and during the first four weeks of the study. In addition, photographs of the entire body will be taken in equipped sites using a whole-body imaging device.

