6.5 Study drug discontinuation

The study drug must be permanently discontinued when any of the following conditions is reported for a subject during the clinical trial:

- Serious immediate-type allergic manifestations including anaphylactic reaction
- Diagnosis of a malignancy (except curatively treated *in situ* cervical carcinoma or basal cell carcinoma)
- Pregnancy
- Any opportunistic infection (such as active TB and other infections whose nature or course suggest an immune-compromised status)
- Other systemic rescue therapies for PN (such as cyclosporine, thalidomide, gabapentin, phototherapy)
- Asthma/ worsening of asthma reported as a serious adverse event

In the event that the study drug is discontinued, the subjects should remain in the study and will be asked to return for all remaining visits and all assessments (including daily assessments of pruritus and sleep disturbance) according to [Table 2](#), except those who withdraw their consent for study participation or in case of pregnancy.

In the event of a missed dose (i.e. temporary discontinuation of the study drug), it will be documented in the eCRF that the drug has not been administered at the study visit, together with the reason (e.g. for safety reason). Subjects will be asked to return to the investigational sites for all remaining visits and complete all study assessments and procedures as described in Table 2.

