8.1.3 Follow up period

8.1.3.1 Visit 9 / Day 113, Week 16 (+/- 5 days)

The Investigator or designee will:

1. Collect information regarding AE (including review of laboratory values) and concomitant therapies/procedures.
2. Perform vital signs measurements.
3. Complete urine pregnancy test for female of childbearing potential only.
4. Conduct respiratory medical assessments, including PEF for subjects with a history of asthma.
5. Collect blood samples for PK, ADA
6. Control the good healing of biopsies when applicable.
7. Check subject's record for pruritus NRS and VRS and remind subject to complete them daily
8. Schedule the next visit for Visit 10.

8.1.3.2 *Visit 10 / Day 126, Week 18 (+/- 7 days)*

The Investigator or designee will:

1. Collect information regarding AE (including review of laboratory values) and concomitant therapies/procedures.
2. Check subject's record for pruritus NRS and VRS.
3. Perform physical examination & vital signs measurements.
4. Complete urine pregnancy test for female of childbearing potential only.
5. Conduct respiratory medical assessments, including PEF for subjects with a history of asthma.
6. Complete the evaluation of PAS and IGA.
7. Collect blood samples for PK, ADA
8. Take whole body photographs (selected centers only).
9. Collect the device used for Pruritus assessments
10. Complete the exit form.

8.1.4 *Early Termination visit or unscheduled visit:*

The Investigator or designee will:

1. Collect information regarding AE (including review of laboratory values) and concomitant therapies/procedures.
2. Check subject's record for pruritus NRS and VRS.
3. Ask subject to complete the DLQI.

4. Complete the evaluation of PAS and IGA.
5. Perform physical examination & vital signs measurements and ECG.
6. Conduct respiratory medical assessments, including PEF for subjects with a history of asthma.
7. Complete urinalysis.
8. Complete urine pregnancy test for female of childbearing potential only.
9. Collect blood samples for hematology & biochemistry
10. Collect blood samples for PK and ADA.
11. Complete the exit form in case of early termination and collect e-devices.

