9.3.2 Assumptions

VAS and NRS are considered highly correlated (Reich et al 2012), thus all estimators for VAS are assumed to be the same for NRS.

For the current study, it is assumed that the common standard deviation is 35 and that the true difference between Nemolizumab and the placebo is 30% in terms of percent change from baseline in worst itching score on a NRS at Week 4.

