9.3.3 Sample size calculation

With an effect size of (30/35=) 0.857, a power of 90% and a type I error of 5% two-sided; at least 30 subjects are needed per group. In order to maintain the power of the tests, for per-protocol population, in case of drop outs/major deviations at Week 4, the sample size will be increased to 35 subjects per group, i.e. 70 to be randomized.

9.4 Interim analysis at Week 4

An interim analysis may be performed once at least 40 subjects will have completed the week 4 visit or discontinued before (decision will be taken by the Sponsor according to the recruitment rate). This analysis will include efficacy data on all subjects up to that time point. In addition to efficacy, all safety data available (not only data up to week 4) will also be analyzed. This interim analysis may be performed to inform the Sponsor for the subsequent clinical program. Blind will be broken for a limited Galderma R&D Staff involved in this trial according to the communication plan. The study will remain blinded to Investigators, CRO clinical team and sites staffs, as no results will be sent out. Furthermore, only summary statistics (by treatment) and

individual listings (without treatment identity) will be provided for this analysis. This will avoid individual unblinding. No discontinuation rules have been defined for this study based on the outcome of this interim analysis.

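### Exit before Week 4: sections 5.8 and 6.5 are not reconciled and 8.1.4 takes back the itch diary, so some primary values are imputed that could have been recorded

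*Protocol*

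**What the plan says.** **Stopping drug (protocol 6.5).** "In the event that the study drug is discontinued, the subjects should remain in the study", attending every remaining visit and completing every assessment, the daily itch rating included. Two groups are exempt: "except those who withdraw their consent for study participation or in case of pregnancy".

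**Leaving the study (protocol 5.8).** The section first separates leaving the study from stopping treatment only, and refers the latter to 6.5. It then adds, without criteria, "Investigators or the sponsor can also withdraw subjects from the clinical trial if deemed to be necessary". Its list of reasons reads: "Potential reasons for study discontinuation include pregnancy, consent withdrawal by the subject, lost to follow-up, lack of efficacy, AEs, protocol deviations and others". The list does not say who decides. The section foresees drug and study stopping at the same time and asks only that the two reasons match.

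**Visits after exit (protocol 5.8 and 8.1.4).** A subject who exits before Week 4 has an early termination visit and a final visit 10 weeks after the last injection. After Week 4, 5.8 asks only for the final visit. Item 11 of 8.1.4 reads: "Complete the exit form in case of early termination and collect e-devices".

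**Primary value (SAP 4.2.1.1, 5.2, 5.7, 5.7.1.3).** The Week 4 value is the mean of diary Days 22–28 and is missing with fewer than five entries. LOCF is the primary imputation. The alternatives for continuous endpoints are observed cases and multiple imputation under missing at random.

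**The concern.** Anyone who leaves the study before Week 4 also stops drug, because the Week 4 and Week 8 injections are still due. Both sections then apply to that subject. Section 6.5 would keep the itch diary going. Section 5.8 allows an exit, and 8.1.4 takes the diary away. Nothing says which rule prevails for a subject who still consents.

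The primary endpoint is recorded at home and needs no visit. The protocol itself marks Week 4 as the primary-endpoint visit, yet the procedure can remove the only instrument that records the endpoint from someone who is due back weeks later.

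Exit for poor response or an adverse event may depend on outcome, and perhaps on arm. LOCF and missing-at-random imputation do not address loss that depends on the unseen Week 4 value. The SAP names a missing-not-at-random approach only for binary endpoints.

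**Working it through.** **1. The planned size reproduces.** Inputs: "it is assumed that the common standard deviation is 35 and that the true difference between Nemolizumab and the placebo is 30" points of percent change (protocol 9.3.2); "a power of 90% and a type I error of 5% two-sided; at least 30 subjects are needed per group" (9.3.3); "Subjects meeting inclusion/exclusion criteria will be randomized in a 1:1 ratio to nemolizumab or placebo" (3.1).

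- Normal approximation: n = 2 × (1.960 + 1.282)² × (35/30)² = 28.6, so 29 per group.
- Noncentral t: 30 per group gives 90.4% power, which matches the plan's 30.
- Allowance: 35 − 30 = 5 per group, and 5/35 = 14.3%.

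**2. When the Week 4 value is lost.** The window is Days 22–28 and the minimum is five entries. With no missed days:

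| Last diary day | Entries in window | Week 4 value |
|---|---|---|
| 21 | 0 | missing |
| 24 | 3 | missing |
| 25 | 4 | missing |
| 26 | 5 | available |
| 28 | 7 | available |

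The device is therefore needed through Day 26. The itch rating that Table 2 appears to mark at early termination adds at most one entry.

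**3. What is carried forward.** This assumes that LOCF works on the weekly means. SAP 5.2 assigns Days 1–7 to Week 1 and Days 8–14 to Week 2; Days 15–21 belong to no analysis visit. With the five-entry minimum:

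- last diary day 12 to 25: the Week 2 mean is carried;
- last diary day 5 to 11: the Week 1 mean is carried;
- last diary day before 5: there is no post-baseline weekly mean to carry.

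**4. The subject is still due back.** After one dose on Day 1, the final visit falls on Day 1 + 70 = Day 71, which is 71 − 28 = 43 days after the Week 4 window closes.

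**5. Size if lost values are simply dropped.** Standard error = 35 × √(2/n): 8.37 for n = 35 and 9.04 for n = 30. Two-sided 5% t-test, difference 30:

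| Lost per arm | n per arm | Power |
|---|---|---|
| 0 | 35 | 94.2% |
| 2 | 33 | 92.9% |
| 5 | 30 | 90.4% |
| 7 | 28 | 88.3% |
| 10 | 25 | 84.4% |

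**6. Size under LOCF.** Here n stays at 35, but the difference may shrink. Let d be the fraction of subjects imputed and f the share of the Week 4 effect that the carried values hold. The difference is then 30 × [1 − d(1 − f)]. The documents give neither d nor f, so both are assumptions; the SD stays at 35.

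| d | f = 0 | f = 0.5 | f = 1 |
|---|---|---|---|
| 10% | 27.0 (88.9%) | 28.5 (91.9%) | 30.0 (94.2%) |
| 20% | 24.0 (80.7%) | 27.0 (88.9%) | 30.0 (94.2%) |

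This covers dilution only. Selective exit could move the estimate either way, and the documents give nothing from which to size that.

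**The case against.** The strongest defence is that 5.8 and 6.5 describe two different pathways. Section 5.8 says so at its start, and 6.5 already has the retention rule one would want for subjects who stop only the drug. That stands. What is left is the overlap when both stop together, which 5.8 foresees without saying how 6.5 applies.

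Other limits also stand. The loss occurs only if the device is collected before about Day 26. The later follow-up is one safety visit, not the full schedule. The subject stays in the ITT analysis with an imputed value. The SAP is based on protocol Amendment 2.0 of 09 Apr 2018, whereas the protocol supplied is V00, so later wording may differ.

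A reader might infer more than the documents support:

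- **That the investigator or sponsor may remove consenting subjects specifically for lack of efficacy, adverse events or deviations.** The power to withdraw and the list of reasons are separate sentences. Section 5.8 also has an adverse event recorded as the reason in place of subject withdrawal when it led to the exit, so some of these exits are the subject's own choice.
- **That 14% of primary values will be lost this way, with a bias that can be stated in points.** The allowance covers dropouts and major deviations together, for the per-protocol population, and major deviators may have complete diaries. No document gives an exit rate or the gap between carried and true values.
- **That the same mechanism reaches Weeks 8 to 18.** After Week 4, 5.8 requires no early termination visit, so collection of the device is not clearly triggered.
- **That adverse events and lack of efficacy should be recorded only as reasons for stopping drug.** That would conflict with 5.8's own recording rule and with the SAP outputs on study discontinuation by reason (5.3.1) and on adverse events leading to study discontinuation (5.8.3).

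**Conclusion.** The point holds in a limited form. In protocol V00, 5.8, 6.5 and 8.1.4 do not together settle what happens to a consenting subject who stops drug and study before Week 4. Followed as written, the early termination procedure makes the primary value missing when the diary is returned before about Day 26, although that value could still have been recorded at home.

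The number affected is unknown. Power is not the main issue: with the planned five per arm lost it is 90.4%. It falls to about 81% only if one subject in five is imputed and the carried values hold none of the effect, and nothing in the documents supports that combination. The harm is avoidable imputation of the primary endpoint in subjects whose exit may be related to outcome, with no sensitivity analysis for the continuous endpoint that allows for this. It is a cheap improvement to make, not a flaw that invalidates the design. The conclusion assumes that the V00 wording still applies and that some of these subjects would agree to go on rating their itch.

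**What to change.** 1. **Protocol 8.1.4, item 11.** Let subjects with an early termination visit before Day 29 who still agree to data collection keep the e-diary through Day 28. They return it at the final visit that 5.8 already schedules. State in the SAP that these entries count in the ITT analysis; entries after rescue would still follow the SAP's existing rule.
2. **Protocol 5.8 and 6.5.** Reconcile the two sections so that a subject who stops drug and has not withdrawn consent is by default asked to continue the assessments. Leave the pregnancy exception in 6.5 as it is. For any actual study exit, keep recording the true reason, including adverse event or lack of efficacy.

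Change 1 is worth making even if 5.8 is left alone. Neither change affects when study drug is stopped or the right to withdraw consent.

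**Cost.** Protocol wording, one SAP sentence, and devices out some weeks longer for a few subjects, with some risk that they come back late. No visit or procedure is added; the subject is asked for daily ratings through Day 28.
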